10.1.11. Publication Policy

- The results of this study may be published or presented at scientific meetings. If this is foreseen, the investigator agrees to submit all manuscripts or abstracts to the sponsor before submission. This allows the sponsor to protect proprietary information and to provide comments.
- The sponsor will comply with the requirements for publication of study results. In accordance with standard editorial and ethical practice, the sponsor will generally support publication of multicentre studies only in their entirety and not as individual site data. In this case, a coordinating investigator will be designated by mutual agreement.
- Authorship will be determined by mutual agreement and in line with International Committee of Medical Journal Editors authorship requirements.
- GSK seeks to publish medically or scientifically significant results in searchable peer-reviewed scientific literature within 18 months from LSLV. We follow International Committee of Medical Journal Editors standards for authorship and use Good Publications practices to guide our publications.

10.2. Appendix 2: Clinical Laboratory Tests

- The tests detailed in [Table 8](#) will be performed by the central laboratory, and, in certain cases, by the local laboratory.
- Protocol-specific requirements for inclusion or exclusion of participants are detailed in [Section 5](#).
- Additional tests may be performed at any time during the study as determined necessary by the investigator or required by local regulations.

Table 8 Protocol-Required Safety Laboratory Tests

Laboratory Assessments	Parameters				
Haematology ¹	Platelet Count	RBC Indices: MCV MCH %Reticulocytes		WBC count with Differential : Neutrophils Lymphocytes Monocytes Eosinophils Basophils	
	RBC Count				
	Haemoglobin				
	Haematocrit				
Clinical Chemistry ^{2, 3}	BUN	Potassium	AST/ SGOT		Total and direct bilirubin
	Creatinine	Sodium	ALT/ SGPT		Total Protein
	Glucose	Calcium	Alkaline phosphatase ³		
Routine Urinalysis ⁴	
• Specific gravity• pH, glucose, protein, blood, ketones by dipstick• Microscopic examination (if blood or protein is abnormal)				
Pregnancy testing ⁵	
• Highly sensitive serum or urine hCG pregnancy test (as needed for females of childbearing potential)				
Other Screening Tests	
• Serology (hepatitis B surface antigen [HBsAg], and hepatitis C virus antibody)• All study-required laboratory tests will be performed by a central laboratory, with the exception of parasitic screening, urinalysis and urine pregnancy tests.
○ Parasitic Screening is only required in regions with high-risk or for participants who have visited high-risk regions in the past 6 months. Sites should use local laboratories where available. If no local laboratories are available, the tests should be performed centrally.○ If central laboratories are used, stool microscopy test for ova and parasites is done. The organisms detected by this test can be viewed in the SRM. It is important to note that the test provided by the central laboratory will only detect the organisms listed. If the				

Laboratory Assessments	Parameters
	
participant may potentially carry any parasitic infection not covered by the central laboratory test, then the investigator is required to arrange any specialist reviews or alternative testing (using local laboratories).
 
 • PK, immunogenicity, and biomarker tests

Abbreviations: ALT, alanine aminotransferase; AST, aspartate aminotransferase; BUN, blood urea nitrogen; HBsAg, hepatitis B surface antigen; hCG, human chorionic gonadotropin; INR, international normalised ratio; MCH, mean corpuscular haemoglobin; MCV, mean corpuscular volume; PK, pharmacokinetic; RBC, red blood cell; SGOT, serum glutamic oxaloacetic transaminase; SGPT, serum glutamic pyruvic transaminase; ULN, upper limit of normal; WBC, white blood cell.

NOTES:

1. Eosinophil count may be tested locally for screening visit 1 only. If a local sample is required, it is important that a sample for central analysis is obtained at the same time.
Local lab eosinophil count results performed at the screening visit (visit 1) will be entered to the eCRF. If local lab samples are taken, a second sample will also be sent for central testing, with the higher of the eosinophil cell count values to be used to fulfil the entry criteria for enrolment.
2. Details of liver chemistry stopping criteria and required actions and follow-up assessments after liver stopping or monitoring event are given in Section 7.1 and Section 10.5 All events of ALT $\geq 3 \times$ upper limit of normal (ULN) and total bilirubin $\geq 2 \times$ ULN ($>35\%$ direct bilirubin) or ALT $\geq 3 \times$ ULN and international normalized ratio (INR) >1.5 , if INR measured, which may indicate severe liver injury (possible Hy's Law), must be reported as an SAE (excluding studies of hepatic impairment or cirrhosis).
3. If alkaline phosphatase is elevated, consider fractionating.
4. If found abnormal, the urine sample will be sent to the central laboratory for further testing.
5. Local urine testing will be standard for the protocol unless serum testing is required by local regulation or IRB/EC. If a test cannot be confirmed as negative (e.g., an ambiguous result), a serum pregnancy sample will be sent to the central laboratory for further testing.

10.3. Appendix 3: AEs and SAEs: Definitions and Procedures for Recording, Evaluating, Follow-up, and Reporting

10.3.1. Definition of AE

AE Definition

 An AE is any untoward medical occurrence in a clinical study participant, temporally associated with the use of a study intervention, whether or not considered related to the study intervention. 
NOTE: An AE can therefore be any unfavourable and unintended sign (including an abnormal laboratory finding), symptom, or disease (new or exacerbated) temporally associated with the use of a study intervention.

Events Meeting the AE Definition

 Any abnormal laboratory test results (haematology, clinical chemistry, or urinalysis) or other safety assessments (e.g., ECG, radiological scans, vital signs measurements), including those that worsen from baseline, considered clinically significant in the medical and scientific judgement of the investigator (i.e., not related to progression of underlying disease). Exacerbation of a chronic or intermittent pre-existing condition including either an increase in frequency and/or intensity of the condition. New conditions detected or diagnosed after study intervention administration even though it may have been present before the start of the study. Signs, symptoms, or the clinical sequelae of a suspected intervention- intervention interaction. Signs, symptoms, or the clinical sequelae of a suspected overdose of either study intervention or a concomitant medication. Overdose per se will not be reported as an AE/SAE unless it is an intentional overdose taken with possible suicidal/self-harming intent. Such overdoses should be reported regardless of sequelae. "Lack of efficacy" or "failure of expected pharmacological action" per se will not be reported as an AE or SAE. Such instances will be captured in the efficacy assessments. However, the signs, symptoms, and/or clinical sequelae resulting from lack of efficacy will be reported as AE or SAE if they fulfil the definition of an AE or SAE. The signs, symptoms, and/or clinical sequelae resulting from lack of efficacy will be reported as AE or SAE if they fulfil the definition of an AE or SAE. "Lack of efficacy" or "failure of expected pharmacological action" also constitutes an AE or SAE.

Events NOT Meeting the AE Definition

 Any clinically significant abnormal laboratory findings or other abnormal safety assessments that are associated with the underlying disease, unless judged by the investigator to be more severe than expected for the participant's condition. The disease/disorder being studied or expected progression, signs, or symptoms of the disease/disorder being studied, unless more severe than expected for the participant's condition. Medical or surgical procedure (e.g., endoscopy, appendectomy): the condition that leads to the procedure is the AE. Situations in which an untoward medical occurrence did not occur (social and/or convenience admission to a hospital). Anticipated day-to-day fluctuations of pre-existing disease(s) or condition(s) present or detected at the start of the study that do not worsen.

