8.1.1. HES Flare

A HES flare is defined as a HES-related clinical manifestation based on a physician documented change in clinical signs or symptoms (worsening symptoms and/or elevated blood eosinophil level) resulting in the need for either of the following:

- An increase from the most recent dose in the maintenance OCS dose (prednisone/prednisolone equivalent) by at least 10 mg/day for 5 days
- An increase in or addition of any immunosuppressive and/or cytotoxic HES therapy from/to the most recent dose of HES therapy.

To be considered as a HES flare, the most recent dose of HES therapy must not have changed for at least 4 weeks prior to the flare. This ensures that failed reductions in HES therapy are not misclassified as a HES flare.

The start date for a HES flare will be defined as the date of therapy escalation confirmed by the investigator attributable to a HES-related clinical manifestation.

When a participant experiences a HES flare, the investigator will monitor the change in disease control per routine medical care (e.g., follow-up call) and record the resolution of the flare including the end date. Investigators are encouraged, as medically appropriate, to return the participant's treatment regimen to the level prior to the flare after the flare has resolved.

In the event of disease worsening for which the investigator suspects a HES flare between scheduled clinic visits, when possible, the participant will return to the clinic to have the unscheduled 'Flare' visit assessment completed as described in the SoA. When attending the clinic visit at the time of a suspected HES flare is not possible, the investigator should make every effort to evaluate the participant via telephone and complete the CCI [REDACTED]. If an escalation of therapy is initiated by a non-study physician, the investigator should confirm that the escalation in therapy is attributable to a HES-related clinical manifestation.

CCI

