4.2.1. Definition of endpoint/estimands

Definition of HES flare:

A HES flare is defined as a HES-related clinical manifestation based on a physician documented change in clinical signs or symptoms (worsening symptoms and/or elevated blood eosinophil level) resulting in the need for either of the following:

- An increase from the most recent dose in the maintenance OCS dose (prednisone/prednisolone equivalent) by at least 10 mg/day for 5 days.
- An increase in or addition of any immunosuppressive and/or cytotoxic HES therapy from/to the most recent dose of HES therapy.

To be considered as a HES flare, the most recent dose of HES therapy must not have changed for at least 4 weeks prior to the flare. This ensures that failed reductions in HES therapy are not misclassified as a HES flare.

The start date for a HES flare will be defined as the date of therapy escalation confirmed by the investigator attributable to a HES-related clinical manifestation.

Derivation of Endpoint

HES flares are recorded by the investigators in the HES flares details form. The number of observed HES flares will be calculated for each participant as the number of unique starting dates for HES flares which occur at least 14 days after the date of resolution from any preceding HES flare. Both on- and off-treatment flares will be included within the analysis of the primary endpoint, however any post-treatment flares recorded will not be included (see Section 6.2.2.1).

Primary Estimand

The primary estimand is described in Section 1.1 and summarised below.

Target Participant Population	Participants with HES aged 6 to 17 years with or without maintenance SoC therapy.
Primary Endpoint	Frequency of HES flares over 52 weeks.
Intercurrent events	The anticipated intercurrent events and corresponding strategies are:- 
 • Study treatment discontinuation: treatment policy strategy. • Change to background HES medication which might modulate the disease course of HES, determined either by published data or by proposed or known mechanism of action (other than changes due to a clinically documented flare): treatment policy strategy.
Summary measure	Annualised rate of HES flares.

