4.7.2. Adverse Events

Summary of adverse events (AEs), Serious (SAEs) and other significant AEs will be based on GSK Core Data Standards. AEs will be summarised for all participants by treatment group and overall.

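### The AE definition says both that lack of efficacy is not reported as an AE and that it is one, so HES flares may be classified inconsistently in the safety data

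*Protocol*

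**What the plan says.** The text is in the AE definition table of Protocol 10.3.1, in the part listing events that meet the definition.

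- Lack of efficacy, or failure of the expected pharmacological action, "per se will not be reported as an AE or SAE. Such instances will be captured in the efficacy assessments".
- Signs, symptoms and sequelae "resulting from lack of efficacy will be reported as AE or SAE if they fulfil the definition of an AE or SAE". This sentence appears twice in succession.
- The block then closes by stating that lack of efficacy, or failure of the expected action, "also constitutes an AE or SAE".

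Two further entries in 10.3.1 bear on a worsening of HES. The list of events that are AEs includes: "Exacerbation of a chronic or intermittent pre-existing condition including either an increase in frequency and/or intensity of the condition". The list of events that are not AEs includes: "The disease/disorder being studied or expected progression, signs, or symptoms of the disease/disorder being studied, unless more severe than expected".

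Flares are defined separately, in Protocol 8.1.1: "A HES flare is defined as a HES-related clinical manifestation based on a physician documented change in clinical signs or symptoms", leading to a specified escalation of therapy. SAP 4.2.1 says where they are captured: "HES flares are recorded by the investigators in the HES flares details form". On the safety side, SAP 4.7.2 says: "Summary of adverse events (AEs), Serious (SAEs) and other significant AEs will be based on GSK Core Data Standards". The visible SAP text has no rule for including, excluding or separately tabulating AEs that are also flares.

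**The concern.** Two sentences in one table give opposite answers to the same question, and the duplicated sentence between them suggests that two alternative template wordings were both left in. The question matters here because the primary efficacy event is itself a worsening of the disease. An investigator who sees a flare has one sentence pointing to the efficacy forms only and another pointing to the AE form as well.

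Several safety outputs would be exposed:

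- The AE and SAE summaries, and the table of AEs leading to discontinuation or withdrawal (Protocol 9.4.4). Protocol 7.1 lists AE and lack of efficacy as separate reasons for stopping treatment; under the closing sentence of 10.3.1 they are no longer separate.
- The summary of on-treatment AEs by anti-drug antibody result (SAP 4.8.1).
- SAE reporting within 24 hours (Protocol 8.3.1). A flare that leads to hospitalisation meets a seriousness criterion in Protocol 10.3.2 if it is an AE at all.

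With about 15 participants and no control arm, a few records handled differently would change the percentages visibly, and no comparison group would reveal it.

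**Working it through.** No sample-size or power figure depends on this point. The check is a comparison of texts, followed by arithmetic for scale only.

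**Step 1. The statements side by side**

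| Text in Protocol 10.3.1 | Effect on lack of efficacy | Effect on a HES flare |
|---|---|---|
| Lack-of-efficacy exclusion | Not an AE/SAE in itself | Points away from reporting, if the flare is seen as lack of efficacy |
| Sequelae sentence (twice) | Sequelae reported if they qualify | Depends on the general AE definition |
| Closing sentence | Is an AE/SAE | Points towards reporting, if the flare is seen as lack of efficacy |
| Exacerbation entry | Silent | Points towards reporting |
| Disease-under-study exclusion | Silent | Points away, unless more severe than expected |

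Rows 1 and 3 cannot both hold. Rows 4 and 5 conflict for a flare, because a flare is a documented worsening of the disease under study. Whether it is more severe than expected is left to judgement.

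**Step 2. Does another section settle it?** Protocol 8.1.1 defines a flare but does not say whether it is an AE. Protocol 10.3.4 prefers the diagnosis to individual signs and symptoms as the AE term, so a site reporting flare symptoms is steered towards entering the flare itself. SAP 4.7.2 has no separating rule. Nothing visible settles it.

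**Step 3. Scale**

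Inputs, from Protocol 9.2 and SAP 5: N = 15; planning rate 0.26 per year; 95% CI 0.07 to 0.93. Assumptions: one year of follow-up each, and one AE record per flare if flares are recorded.

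The stated interval implies a log-scale standard error of ln(0.93/0.07)/(2 × 1.96) = 0.660. Around 0.26 this gives 0.071 to 0.948. The upper limit is slightly above 0.93 because 0.26 is rounded; the geometric mean of the stated limits is 0.255. This is a consistency check only, since the dispersion is not given.

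Expected flares = N × rate × 1 year.

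Participants with at least one flare:
- Poisson: N × (1 − e^(−rate)).
- Negative binomial: N × (1 − (1 + k × rate)^(−1/k)), with k = 15 × 0.660² − 1/0.26 = 2.7. This k is back-solved and is an assumption; rounding of the limits allows 2.3 to 3.1.

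| Rate per year | Expected flares | Participants with ≥1, negative binomial | Participants with ≥1, Poisson |
|---|---|---|---|
| 0.07 | 15 × 0.07 = 1.05 | 0.9 (6%) | 1.0 (7%) |
| 0.26 | 15 × 0.26 = 3.9 | 2.7 (18%) | 3.4 (23%) |
| 0.93 | 15 × 0.93 = 13.95 | 5.6 (37%) | 9.1 (61%) |

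At each rate, these are the most that the expected flare-related AE count could differ between recording every flare and recording none. Worsening that falls short of the flare definition is not counted here.

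**The case against.** The strongest defence is that the rule closest to a flare is the disease-under-study exclusion, not the lack-of-efficacy text. An investigator who applies that exclusion keeps most flares off the AE form whatever the stray sentence says, and no passage defines a flare as lack of efficacy. The CRF guidelines and study reference manual, which are not available here, may also give an instruction. The primary endpoint comes from the flare form, and there is no hypothesis test or between-group safety comparison to distort.

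Much of this stands, and it limits the consequence. It does not remove the contradiction: the exacerbation entry and the closing sentence point the other way, and the severity exception is a matter of judgement.

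Four stronger readings are tempting but not supported:

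- A reader might infer that flares will inflate AE and SAE counts at some sites and not at others. Nothing in the documents shows that sites will diverge, only that the text allows it.
- A reader might contrast every flare being an AE with none being one. The exclusion does not give zero, because qualifying signs, symptoms and sequelae are still reported.
- A reader might take 2 flares per year from the entry criterion and reach 15 × 2 = 30 records. That rate is a pre-study minimum under a looser definition (Protocol 5.1), without the 10 mg/day for 5 days threshold and without the stable-dose requirement for every flare. It is more than double the upper planning limit of 0.93.
- A reader might conclude that drug-related AE tables and the monitoring committee's review are compromised. Causality is a separate investigator judgement (Protocol 10.3.4), seriousness needs its own criterion (10.3.2), and the committee's summaries are specified in a separate plan and charter that cannot be seen here.

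**Conclusion.** Protocol 10.3.1 is wrong as written: it both excludes and includes lack of efficacy, and nothing visible in either document decides between them. Together with the unreconciled exacerbation and disease-under-study entries, this means that flares and other efficacy failures may be classified inconsistently as AEs or SAEs across investigators. The exposure is limited to the safety summaries and SAE reporting; the primary flare rate is unaffected.

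The size is modest in absolute terms but not negligible for 15 participants: at most about 4 flare records in about 3 participants at the planning rate, and about 1 to 14 records across the planning interval. SAE counts would change only for flares that also meet a seriousness criterion. Confidence is high for the textual contradiction. The consequence is a possibility, and its scale rests on the adult and adolescent extension study's rate applying here and on one record per flare.

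**What to change.** 1. The sponsor confirms which rule is intended. The exclusion is the one consistent with the disease-under-study entry in 10.3.1 and with the separate discontinuation reasons in 7.1.
2. If so, delete the closing sentence that makes lack of efficacy an AE or SAE, and the second copy of the signs-and-symptoms sentence before it.
3. Reconcile the exacerbation entry with the disease-under-study exclusion by stating explicitly whether a protocol-defined HES flare is recorded as an AE, and that the SAE criteria are applied separately. Deletion alone would settle lack of efficacy but not flares.
4. Add one line to SAP 4.7.2 saying how any flare-related AEs are tabulated, for example within the main tables with a separate count.
5. Before database lock, compare reported AE terms and dates with the flare form and query mismatches under the confirmed rule.

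The cost is a protocol clarification letter, one SAP sentence, one data-review check and some queries to sites on AE terms already entered. No assessment or visit changes.

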10.3.2. Definition of SAE

An SAE is defined as any untoward medical occurrence that, at any dose, meets one or more of the criteria listed:
a. Results in death
b. Is life-threatening The term 'life-threatening' in the definition of 'serious' refers to an event in which the participant was at risk of death at the time of the event. It does not refer to an event, which hypothetically might have caused death, if it were more severe.
c. Requires inpatient hospitalisation or prolongation of existing hospitalisation 
 In general, hospitalisation signifies that the participant has been admitted (usually involving at least an overnight stay) at the hospital or emergency ward for observation and/or treatment that would not have been appropriate in the physician's office or outpatient setting. Complications that occur during hospitalisation are AE. If a complication prolongs hospitalisation or fulfils any other serious criteria, the event is serious. When in doubt as to whether "hospitalisation" occurred or was necessary, the AE should be considered serious. Hospitalisation for elective treatment of a pre-existing condition that did not worsen from baseline is not considered an AE.
d. Results in persistent or significant disability/incapacity 
 The term disability means a substantial disruption of a person's ability to conduct normal life functions.

An SAE is defined as any untoward medical occurrence that, at any dose, meets one or more of the criteria listed:	

 This definition is not intended to include experiences of relatively minor medical significance such as uncomplicated headache, nausea, vomiting, diarrhoea, influenza, and accidental trauma (e.g., sprained ankle) which may interfere with or prevent everyday life functions but do not constitute a substantial disruption. 	
e.	Is a congenital anomaly/birth defect
f.	Other situations: 
 Possible Hy's Law case: ALT\geq3xULN AND total bilirubin \geq2xULN (>35% direct bilirubin) or international normalized ratio (INR) >1.5 must be reported as SAE Medical or scientific judgement should be exercised by the investigator in deciding whether SAE reporting is appropriate in other situations such as significant medical events that may jeopardise the participant or may require medical or surgical intervention to prevent 1 of the other outcomes listed in the above definition. These events should usually be considered serious. 
 Examples of such events include invasive or malignant cancers, intensive treatment for allergic bronchospasm, blood dyscrasias, convulsions, or development of intervention dependency or intervention abuse.

